11.1. Analysis Sets

Full Analysis Set: The full analysis set will include all randomized participants with at least one study intervention administration documented. Participants will be analyzed according to the intervention they actually received.

Per-protocol Immunogenicity Population: The per-protocol immunogenicity population will include all randomized and vaccinated participants for whom immunogenicity data are available excluding participants with major protocol deviations expecting to impact the immunogenicity outcomes (eg, missed vaccinations, natural infections, etc).

11.2. Sample Size Determination

The sample size is not based on formal hypothesis testing considerations. Active control recipients are included for blinding purposes and safety analyses, and will provide control specimens for immunologic assays.

The sample size for this study expands the safety and immunogenicity database for VAC52150 to infants. While mild to moderate vaccine reactions (local/systemic responses) are expected, adverse events that preclude further study intervention administration or more serious events that would limit product development are not anticipated:

- When 73 infants are vaccinated with Ad26.ZEBOV, MVA-BN-Filo, the observation of 0 reactions would be associated with a 95% confidence that the true rate is less than 4.0%.
- When 34 infants are vaccinated with active control, the observation of 0 reactions would be associated with a 95% confidence that the true rate is less than 8.4%.

Table 3 provides the probabilities of observing at least one adverse event at given true adverse event rates.

	Probability of Observing at Least One Adverse Event (%)		
True Adverse Event Incidence (%)	Ad26.ZEBOV, MVA-BN-Filo N=73	Active Comparator N=34	
1	52	29	
3	89	64	
5	98	83	
7	99	92	
9	100	96	
15	100	100	

Table 3: Probability of Observing at Least One Adverse Event Given a True Adverse Event Incidence

n: number of participants

11.3. Participant Information

For all participants, demographic characteristics (eg, age, weight and length percentiles according to WHO pediatric growth and weight charts, ²¹ race, and gender), and other baseline characteristics (eg, vital signs, concomitant diseases) will be tabulated and summarized with descriptive statistics.

11.5. Immunogenicity Analyses

No formal hypothesis on immunogenicity will be tested. Descriptive statistics (geometric mean and 95% CI, or median and range Q1-Q3, as appropriate) will be calculated for continuous immunologic parameters at all available time points. Graphical representations of immunological parameters will be made as applicable. Frequency tabulations will be calculated for discrete (qualitative) immunologic parameters as applicable.

11.6. Interim Analysis

The primary interim analysis for the blinded phase of the study will be done when all participants have completed the 12 months post-dose-1 visit or have left the main study (ie, completion of the main study), and the clinical database is locked and unblinded. This analysis will include all available data up to the 12 months post-dose-1 (D365) visit.

11.7. Independent Data Monitoring Committee

An IDMC will be established to monitor data on an ongoing basis to ensure the continuing safety of the participants enrolled in the main study.

The Committee will meet periodically to review newly generated data. Ad hoc IDMC meetings may be requested via the sponsor for any single event or combination of multiple events which are considered to jeopardize the safety of the participants. After the review, the IDMC will make recommendations regarding the continuation of the study. The IDMC responsibilities, authorities, frequency and timing of the evaluations and procedures will be documented in its charter. All analyses that are planned to support the IDMC evaluations will be included in the associated SAP.

All IDMC members will be external and independent of the sponsor, including at least one medical expert in the relevant therapeutic area and at least one statistician.

11.8. Independent Medical Reviewer

An independent medical reviewer will be appointed before the start of the extension phase to review the accumulating safety data on an ongoing basis to ensure the continuing safety of the participants enrolled in the extension phase of the study.

The independent medical reviewer will be consulted periodically to review newly generated data. Ad hoc meetings may be requested via the sponsor if any of the pre-specified pausing rules for this study are met (see Section 9.3.2) or in any situation that could affect the safety of the participants.

After the review, the independent medical reviewer will make recommendations regarding the continuation of the extension phase of the study. The independent medical reviewer responsibilities, authorities, frequency and timing of the evaluations and procedures will be documented in a role and responsibility description.

The independent medical reviewer will be external and independent of the sponsor. He or she will be a medical expert in the relevant field.

12. ADVERSE EVENT REPORTING

Timely, accurate, and complete reporting and analysis of safety information from clinical studies are crucial for the protection of participants, investigators, and the sponsor, and are mandated by regulatory agencies worldwide. The sponsor has established Standard Operating Procedures in conformity with regulatory requirements worldwide to ensure appropriate reporting of safety information; all clinical studies conducted by the sponsor or its affiliates will be conducted in accordance with those procedures.

Method of Detecting Adverse Events and Serious Adverse Events

Care will be taken not to introduce bias when detecting adverse events or serious adverse events. Open-ended and nonleading verbal questioning of the participant's parent(s)/guardian is the preferred method to inquire about adverse event occurrence.

Solicited Adverse Events

Solicited adverse events are predefined local (at the injection site) and systemic events for which the participant's parent(s)/guardian is specifically questioned, and which are noted in the participant's diary.

Unsolicited Adverse Events

Unsolicited adverse events are all adverse events for which the participant's parent/guardian is not specifically questioned in the participant diary.

12.1. Definitions

12.1.1. Adverse Event Definitions and Classifications

Adverse Event

An adverse event is any untoward medical occurrence in a clinical study participant administered a medicinal (investigational or non-investigational) product. An adverse event does not necessarily have a causal relationship with the intervention. An adverse event can therefore be any unfavorable and unintended sign (including an abnormal finding), symptom, or disease temporally associated with the use of a medicinal (investigational or non-investigational) product, whether or not related

to that medicinal (investigational or non-investigational) product. (Definition per International Council for Harmonisation of Technical Requirements for Pharmaceuticals for Human Use [ICH])

This includes any occurrence that is new in onset or aggravated in severity or frequency from the baseline condition, or abnormal results of diagnostic procedures.

Note: For time period of sponsor's adverse event collection, see Section 12.3.1.

Serious Adverse Event

A serious adverse event based on ICH and EU Guidelines on Pharmacovigilance for Medicinal Products for Human Use is any untoward medical occurrence that at any dose:

- Results in death
- Is life-threatening
 (The participant was at risk of death at the time of the event. It does not refer to an event that hypothetically might have caused death if it were more severe.)
- Requires inpatient hospitalization or prolongation of existing hospitalization
- Results in persistent or significant disability/incapacity
- Is a congenital anomaly/birth defect
- Is a suspected transmission of any infectious agent via a medicinal product
- Is Medically Important*

*Medical and scientific judgment should be exercised in deciding whether expedited reporting is also appropriate in other situations, such as important medical events that may not be immediately life threatening or result in death or hospitalization but may jeopardize the participant or may require intervention to prevent one of the other outcomes listed in the definition above. These should usually be considered serious.

If a serious and unexpected adverse event occurs for which there is evidence suggesting a causal relationship between the study intervention and the event (eg, death from anaphylaxis), the event must be reported as a SUSAR (even after the study is over, if the sponsor, IDMC, independent medical reviewer or investigator becomes aware of them).

Unlisted (Unexpected) Adverse Event/Reference Safety Information

An adverse event is considered unlisted if the nature or severity is not consistent with the applicable product reference safety information. For Ad26.ZEBOV and MVA-BN-Filo, the expectedness of an adverse event will be determined by whether or not it is listed in the Investigator's Brochure. For MenACWY, refer to the applicable vaccine prescribing information.

Adverse Event Associated With the Use of the Intervention

An adverse event is considered associated with the use of the intervention if the attribution is related by the definitions listed in Section 12.1.2.

An adverse event is considered not associated with the use of the intervention if the attribution is unrelated by the definitions listed in Section 12.1.2.

12.1.2. Attribution Definitions

Every effort should be made by the investigator to explain any adverse event and to assess its potential causal relationship, ie, to administration of the study intervention or to alternative causes (eg, natural history of an underlying diseases, concomitant therapies). This applies to all adverse events, whether serious or non-serious.

Causality of adverse events should be assessed by the investigator based on the following:

Related: there is suspicion that there is a relationship between study intervention and adverse event (without determining the extent of that probability); there is a reasonable possibility that the study intervention contributed to the adverse event. All adverse events assessed as possibly, probably or definitely related to the study intervention will be considered related to the study intervention.

Unrelated: there is no suspicion that there is a relationship between the study intervention and the adverse event; there are other more likely causes and administration of the study intervention is not suspected to have contributed to the adverse event. All adverse event assessed as unrelated or doubtfully related to the study intervention will be considered unrelated to the study intervention.

By definition, all solicited adverse events at the injection site (local) will be considered related to the study intervention administration.

12.1.3. Severity Criteria

All adverse events, except for solicited adverse events, will be coded for severity using a modified version of the Division of Microbiology and Infectious Diseases (DMID) pediatric grading table (November 2007) (see Appendix 2)⁸.

For adverse events not identified in the table, the following guidelines will apply:

Mild	Grade 1	Symptoms causing no or minimal interference with usual social and functional activities.
Moderate	Grade 2	Symptoms causing greater than minimal interference with usual social and functional activities.
Severe	Grade 3	Symptoms causing inability to perform usual social and functional activities.
Potentially Life- threatening	Grade 4	Any grade 3 symptom that requires hospitalization/in- patient medical intervention.

Note: Only clinically significant abnormalities in laboratory data occurring from signing of the ICF onwards will be reported as adverse events and graded using the table above.

The investigator should use clinical judgment in assessing the severity of events not directly experienced by the participant.

12.2. Special Reporting Situations

Safety events of interest on a sponsor study intervention that may require expedited reporting or safety evaluation include, but are not limited to:

- Overdose of a sponsor study intervention
- Suspected abuse/misuse of a sponsor study intervention
- Medication error involving a sponsor product (with or without participant exposure to the sponsor study intervention, eg, name confusion)

Special reporting situations should be recorded in the CRF. Any special reporting situation that meets the criteria of a serious adverse event should be recorded on the serious adverse event page of the CRF.

12.3. Procedures

12.3.1. All Adverse Events

Symptoms of solicited local and systemic adverse events will be collected in the diary in the evening after the first and second vaccination and then daily for the next 7 days. Unsolicited adverse events will be reported from the first vaccination until 28 days post-dose-1, and from the second vaccination until 28 days post-dose-2.

Serious adverse events and/or special reporting situations that are related to study procedures or that are related to non-investigational (concomitant) sponsor products will be reported from the time a signed and dated ICF is obtained onwards until the end of the study. All other serious adverse events and/or special reporting situations will be reported from the day of the first vaccination onwards until 6 months post-dose-2 in the main study and until 28 days post-dose-2 in the extension phase. The sponsor will evaluate any safety information that is spontaneously reported by an investigator beyond the time frame specified in the protocol.

The investigator will monitor and analyze the study data including all adverse event and clinical laboratory data as they become available and will make determinations regarding the severity of the adverse experiences and their relation to study intervention. All adverse events will be deemed related to study intervention or not related to study intervention, according to Section 12.1.2.

The investigator or clinical designee must review both post-injection reactogenicity and other adverse event CRFs to insure the prompt and complete identification of all events that require expedited reporting as serious adverse events, invoke pausing rules or are other serious and unexpected events.

All adverse events, regardless of seriousness, severity, or presumed relationship to study intervention, must be recorded using medical terminology in the source document and the CRF. Whenever possible, diagnoses should be given when signs and symptoms are due to a common

etiology (eg, cough, runny nose, sneezing, sore throat, and head congestion should be reported as "upper respiratory infection"). Investigators must record in the CRF their opinion concerning the relationship of the adverse event to study therapy. All measures required for adverse event management must be recorded in the source document and reported according to sponsor instructions.

The sponsor assumes responsibility for appropriate reporting of adverse events to the regulatory authorities. The sponsor will also report to the investigator (and the head of the investigational institute where required) all suspected unexpected serious adverse reactions (SUSARs). The investigator (or sponsor where required) must report SUSARs to the appropriate IEC/IRB that approved the protocol unless otherwise required and documented by the IEC/IRB. A SUSAR will be reported to regulatory authorities unblinded. Participating investigators and IEC/IRB will receive a blinded SUSAR summary, unless otherwise specified.

The parent(s)/guardian will be provided with a "wallet (study) card" and instructed to carry this card with their child for the duration of the study indicating the following:

- Study number
- Statement, in the local language(s), that the participant is participating in a clinical study
- Investigator's name and 24-hour contact telephone number
- Local sponsor's name and 24-hour contact telephone number (for medical staff only)
- Site number
- Participant number
- Any other information that is required to do an emergency breaking of the blind
- Ebola prevention counseling

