EUL Emergency Use Listing
EU/mL ELISA units per mL
EVD Ebola virus disease

FANG Filovirus Animal Nonclinical Group

GCP Good Clinical Practice
GMP Good Manufacturing Practice

GP glycoprotein

HITT heparin-induced thrombocytopenia and thrombosis

HIV human immunodeficiency virus

ICF informed consent form

ICH International Council for Harmonisation of Technical Requirements for Pharmaceuticals for

Human Use (previously International Council for Harmonisation)

IDMC Independent Data Monitoring Committee

IEC Independent Ethics Committee

IM intramuscular(ly)

IMI Innovative Medicines Initiative

Inf U infectious units

INSERM Institut National de la Santé et de la Recherche Médicale

IRB Institutional Review Board IWRS interactive web response system

kb kilobase

LSHTM London School of Hygiene and Tropical Medicine

MARV Marburg virus

MedDRA Medical Dictionary for Regulatory Activities

MVA Modified Vaccinia Ankara

MVA-BN-Filo Modified Vaccinia Ankara Bavarian Nordic vector expressing multiple filovirus proteins

NHP nonhuman primate(s) NP nucleoprotein

PCR polymerase chain reaction

PREVAC Partnership for Research on Ebola Vaccination

PQC Product Quality Complaint

RBC red blood cell RNA ribonucleic acid SAP Statistical Analysis Plan

SUDV Sudan virus

SUSAR suspected unexpected serious adverse reaction

TAFV Tai Forest virus

THAM tris (hydroxymethyl)-amino methane

TOU Test of Understanding

TTS thrombosis with thrombocytopenia syndrome

VISP vaccine induced seropositivity

vp viral particles WBC white blood cell

WHO World Health Organization

DEFINITIONS OF TERMS

Study intervention Ad26.ZEBOV, MVA-BN-Filo, or active control (MenACWY)

Independent study intervention monitor

An unblinded study intervention monitor assigned to the study who is responsible for the unblinded interface between the sponsor and the investigational site pharmacy.

Solicited adverse

events

(reactogenicity)

Local and systemic adverse events that are common and known to occur after vaccination and that are usually collected in a standard, systematic format in vaccine clinical studies. For the list of solicited adverse events in this study, see Section 9.3. For the purpose of vaccine clinical studies, all other adverse events are considered unsolicited; however, this definition should be distinguished from definitions based on pharmacovigilance guidelines.

Study Naming Convention

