2. OBJECTIVES, ENDPOINTS, AND HYPOTHESIS

2.1. Objectives and Endpoints

Main Study

Objectives	Endpoints	
Primary		
To assess the safety and reactogenicity of a heterologous 2-dose regimen utilizing Ad26.ZEBOV (first vaccination; Dose 1) and MVA-BN-Filo (second vaccination; Dose 2) administered IM on Days 1 and 57, respectively.	 Solicited local and systemic adverse events until 7 days post-dose-1 and 7 days post-dose-2. Unsolicited adverse events from the first vaccination until 28 days post-dose-1 and from the second vaccination until 28 days post-dose-2. 	
	Any serious adverse events until 6 months post-dose-2, and serious adverse events related to study intervention until end of the study.	
Secondary		
To assess binding antibody responses as measured by ELISA at 21 days post-dose-2.	Binding antibody levels against the EBOV GP using FANG ELISA (EU/mL) at 21 days post-dose-2.	
Exploratory		
To assess binding antibody responses as measured by ELISA at baseline and 12 months post-dose-1.	Binding antibody levels against the EBOV GP using FANG ELISA (EU/mL) at baseline and 12 months post-dose-1.	
To assess the neutralizing antibody response to the adenovirus backbone as measured by Ad26 virus neutralization assay (VNA) at baseline.	Neutralizing antibody levels against the adenovirus backbone using Ad26 VNA at baseline.	

ELISA: enzyme-linked immunosorbent assay, EU/mL: ELISA units/mL; FANG: Filovirus Animal Nonclinical Group.

Extension Phase

Objectives	Endpoints
Primary	
• To provide the heterologous 2-dose vaccination regimen (Ad26.ZEBOV on Day 1 and MVA-BN-Filo on Day 57) to participants in the control arm of the main study.	vaccination regimen (Ad26.ZEBOV on

Objectives	Endpoints	
Exploratory		
To assess the safety and reactogenicity of a heterologous 2-dose vaccination regimen utilizing Ad26.ZEBOV (first vaccination; Dose 1) and MVA-BN-Filo (second vaccination; Dose 2) administered intramuscularly (IM) on Days 1 and 57, respectively.	until 7 days post-dose-1 and 7 days post-dose-2.	
	Any serious adverse events until 28 days post-dose-2.	

Refer to Section 9 for evaluations related to endpoints.

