1.1. Trial Objectives

The objectives of the study and corresponding endpoints are as shown in Table 1. For further details, see the clinical trial protocol $(CTP)^1$

Main study

Table 1:	Study	objectives	and	endpoints
----------	-------	------------	-----	-----------

Objectives	Endpoints
Primary	
• To assess the safety and reactogenicity of a heterologous 2-dose vaccination regimen utilizing Ad26.ZEBOV (first vaccination; Dose 1) and MVA-BN-Filo (second vaccination; Dose 2) administered intramuscularly (IM) on Days 1 and 57, respectively.	 Solicited local and systemic adverse events until 7 days post-dose-1 and post-dose-2. Unsolicited adverse events from the first vaccination until 28 days post-dose-1 and from the second vaccination until 28 days post-dose-2.
	• Any serious adverse events until 6 months post- dose-2, and serious adverse events related to study intervention until the end of the study.
Secondary	
• To assess binding antibody responses as measured by ELISA at 21 days post-dose-2.	• Binding antibody levels against the EBOV GP using FANG ELISA (EU/mL) at 21 days post-dose-2.
Exploratory	
• To assess binding antibody responses as measured by ELISA at baseline and 12 months post-dose-1.	• Binding antibody levels against the EBOV GP using FANG ELISA (EU/mL) at baseline and 12 months post-dose-1.
• To assess the neutralizing antibody response to the adenovirus backbone as measured by the Ad26 virus neutralization assay (VNA) at baseline.	• Neutralizing antibody levels against the adenovirus backbone using Ad26 VNA at baseline.
ELISA: enzyme-linked immunosorbent assay; EU/mL	: ELISA units/mL; FANG: Filovirus Animal Nonclinical

ELISA: enzyme-linked immunosorbent assay; EU/mL: ELISA units/mL; FANG: Filovirus Animal Nonclinical Group.

Objectives	Endpoints
Primary	
• To provide the heterologous 2-dose vaccination regimen (Ad26.ZEBOV on Day 1 and MVA-BN-Filo on Day 57) to participants in the control arm of the main study.	• Completion of the heterologous 2-dose vaccination regimen (Ad26.ZEBOV on Day 1 and MVA-BN-Filo on Day 57).
Exploratory	

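### The SAE reporting rule in Protocol 12.3.1 stops intervention-related SAEs at 6 months post-dose-2, while the primary safety endpoint counts them to the end of the study

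*Protocol*

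**What the plan says.** **Endpoint.** The main-study primary safety endpoint in Protocol 2.1 (also in the synopsis) is "Any serious adverse events until 6 months post-dose-2, and serious adverse events related to study intervention until end of the study". SAP 1.1 agrees, ending with "serious adverse events related to study intervention until the end of the study".

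**Reporting rule.** Protocol 12.3.1 has two parts. SAEs "related to study procedures or that are related to non-investigational (concomitant) sponsor products will be reported" from signed consent to the end of the study. Then, for the main study: "All other serious adverse events and/or special reporting situations will be reported from the day of the first vaccination onwards until 6 months post-dose-2". The same two-part rule stands in the synopsis (study design), footnote n of the main-study Time and Events Schedule, and Sections 1.3.5, 3.1.1, 9.1.3 and 9.3.1. Section 12.1.1 makes 12.3.1 the reference for the period of "adverse event collection, see Section 12.3.1".

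**What happens at the cut-off.** The 6-months post-dose-2 visit (D237) is when all infants are due MenACWY. The Definitions of Terms list study intervention as "Ad26.ZEBOV, MVA-BN-Filo, or active control (MenACWY".

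**Passages that reach further.**
- The schedule marks SAEs at D365, and Section 9.1.4 has that visit check for intervention-related SAEs.
- Section 12.3.2 requires SAEs occurring during the study to be sent to the sponsor within 24 hours, with no 6-month limit, and covers hospitalizations and deaths.
- For a serious, unexpected event with evidence of causality, Section 12.1.1 says that "the event must be reported as a SUSAR (even after the study is over".
- Section 12.3.1 itself requires all adverse events to be recorded and has the sponsor evaluate spontaneous reports made after the time frame. It also has parents "instructed to carry this card with their child for the duration of the study", with a 24-hour telephone number.
- SAP 5.1.1 tabulates SAEs over the whole study.

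**The concern.** A related SAE between the 6-month visit and the 12-month visit belongs to the primary endpoint but falls under the residual category in 12.3.1, whose reporting period has closed. A site working from 12.3.1 or footnote n could treat it as outside required reporting. A site working from 12.3.2 would report it within 24 hours.

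Few other structured safety streams run in those months. Unsolicited AE collection ended 28 days after Dose 2. No diary is issued after the D237 MenACWY dose, and the pausing rules in 9.3.2 exclude that dose. The instruction in 9.1.3 for parents to contact the investigator covers only the period before the 6-month visit. SAP 5.1.4 counts a participant with no reported event as a participant without an event, so an unreported SAE would enter the tables as none.

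**Working it through.** **Step 1: does the rule cover intervention-related SAEs to the end of the study?**

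| SAE category | Protocol 12.3.1, main study | Primary endpoint |
|---|---|---|
| Related to study procedures | to end of study | any SAE to 6 months post-dose-2 |
| Related to non-investigational sponsor products | to end of study | any SAE to 6 months post-dose-2 |
| Related to study intervention | not named, so residual: to 6 months post-dose-2 | **to end of study** |
| Unrelated | residual: to 6 months post-dose-2 | any SAE to 6 months post-dose-2 |

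The third row conflicts. It is not an isolated slip, because the rule appears in seven places with the same categories.

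**Step 2: does 12.3.2 settle it?** No. It covers SAEs during the study whatever their relatedness. It therefore agrees with the endpoint for related SAEs, but it also conflicts with 12.3.1 for unrelated SAEs after 6 months post-dose-2.

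**Step 3: length of the disputed window.** Inputs from the Time and Events Schedule: Dose 2 at D57 ±7 days, 6-month visit at D237 ±30 days, 12-month visit at D365 ±30 days. Visits after a vaccination are timed from the actual vaccination day, and I take the 12-month visit as tied to Dose 1.

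- The schedule's own day reproduces with 6 months taken as 180 days: 57 + 180 = D237.
- Nominal window: 365 − 237 = 128 days; 128/365 = 35%.
- Dose 2 range: 57 ± 7 = D50 to D64.
- Earliest 6-month visit: 50 + 180 − 30 = D200. Latest: 64 + 180 + 30 = D274.
- 12-month visit: 365 ± 30 = D335 to D395.
- Shortest window: 335 − 274 = 61 days. Longest: 395 − 200 = 195 days.
- The 10-day postponement in Section 6.1 could move Dose 2 to D74 and the 6-month visit to D284, leaving 335 − 284 = 51 days. A study pause could shift it further.

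**Step 4: does any stated figure change?** No. The zero-event bounds in Protocol 11.2 reproduce as 1 − 0.05^(1/n): 4.02% for n = 73 (stated 4.0%) and 8.43% for n = 34 (stated 8.4%). They do not depend on the SAE reporting window, and no hypothesis test is planned.

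**The case against.** The strongest reply is that the working parts of the protocol already serve the endpoint. The D365 visit exists partly to check for related SAEs, 12.3.2 has no 6-month cut-off, SUSARs are reportable indefinitely, and 12.3.1 asks for all adverse events to be recorded and provides for late spontaneous reports. This stands as a limit on the harm. A reader might infer that related SAEs after D237 go uncollected; the documents do not support that.

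It does not remove the contradiction. The D365 mark sits in the schedule row governed by footnote n, which states the shorter rule, and 12.1.1 points to 12.3.1 for the collection period.

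Two further replies have some force. First, the end of the study is less open than it looks. Section 1 confines the term study to the main blinded part unless otherwise specified, and Section 10.1 treats an Ebola-arm participant as having completed the study after the 12-month assessments. Both point to D365 for the participant. Even so, 17.10.1 puts study completion at final database lock and 9.3.1 refers to the end of the study phase, so the term should be written out. Second, whether the D237 MenACWY dose counts as study intervention for this endpoint is arguable. The definition lists MenACWY as active control, both arms receive it, and the primary objective concerns the two-dose Ebola regimen. The contradiction does not depend on this, since a late SAE attributed to Ad26.ZEBOV or MVA-BN-Filo is caught in the same way.

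**Conclusion.** The contradiction holds and should be fixed. A primary safety endpoint and the reporting rule meant to supply it disagree for about four months of follow-up: 128 days nominally, and 61 to 195 days across the permitted windows before any postponement or pause. The rule applies to all 107 planned infants, but only an infant with a related SAE in that window could be affected.

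The consequence is a risk of late or inconsistent site reporting. It may be tempting to turn this into a bias in the SAE rate or a shift in an upper confidence bound. The documents give no rate of late related SAEs and no rate of non-reporting, so no such figure can be supported. The window lengths assume 180 days for 6 months, as the schedule implies, and a 12-month visit timed from Dose 1.

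**What to change.** 1. In 12.3.1 and its six repeats (synopsis, schedule footnote n, 1.3.5, 3.1.1, 9.1.3, 9.3.1), add SAEs related to study intervention to the categories reported to the end for the main study.
2. Define the end term by phase. For the main study, use the participant's 12 months post-dose-1 (D365) visit, in both the reporting rule and the endpoint (synopsis, Protocol 2.1, SAP 1.1). This fits Sections 1, 9.1.4 and 10.1. Sections 1.3.5, 9.1.3, 9.3.1 and 12.3.1 also govern the extension phase, which has no D365 visit, so keep a separate extension-phase end term there. Leave unchanged the extension-screening question on SAEs since D365 and the SUSAR rule in 12.1.1.
3. Reconcile 12.3.1 with 12.3.2 explicitly, so that one rule says which SAEs, including unrelated ones, are reportable after 6 months post-dose-2. A sentence saying only that 12.3.1 does not limit 12.3.2 would leave unrelated SAEs under two rules. The reconciliation should not reduce existing duties on deaths, hospitalizations and SUSARs.
4. Optional and minor: extend the parent-contact instruction in 9.1.3 to D365, and align the extension-phase SAE endpoint. SAP 1.1 adds related SAEs to the end of the study; Protocol 2.1 and the synopsis stop at 28 days post-dose-2.

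The cost is wording in the protocol and SAP, with no new visit or procedure. Item 3 needs a sponsor decision on unrelated SAEs, which could affect how many reports sites file.
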